At any time during the treatment period, subjects will be withdrawn from further dosing if they develop any of the following features on MRI: vasogenic edema, macrohemorrhage, an area of superficial siderosis or a symptomatic microhemorrhage. All of these events must be reported on the SAE form with the same reporting requirements as an SAE, but these events are not automatically considered SAEs, except for intracerebral hemorrhages >1 cm, which should always be classified as an important medical event and reported as an SAE even if they do not meet other serious criteria. (revised per Amendments 06 and 20) These subjects will undergo an Early Termination Visit within 7 days after discontinuation and a Follow-Up Visit 3 months after the last dose of treatment. During this interval, they will also undertake an unscheduled visit (with MRI) at approximately 30 days after the visit at which such MRI features were first identified. Additional visits may be arranged if clinically indicated in the opinion of the investigator, and may occur later than 90 days after the final dose of study drug. In addition, subjects who discontinue study drug are required to return after the Early Termination Visit for each scheduled visit when the clinical assessments of efficacy are to be conducted per the Schedule of Procedures/Assessments. (revised per Amendment 06) At these visits, safety information (in addition to efficacy assessments) on concomitant medications, AEs, and SAEs will be collected. (revised per Amendment 01)

Also, at any time during the treatment period, subjects who have nonsymptomatic, treatment-emergent microhemorrhages found on MRI, but none of the features which merit discontinuation of treatment (ie, vasogenic edema, macrohemorrhage, an area of superficial siderosis, or a symptomatic treatment-emergent microhemorrhage) may continue with treatment. These subjects will have safety assessments (including MRI) at approximately 30 days after the visit at which such MRI features were found. They will also continue with the scheduled MRI scans. Additional unscheduled MRI scans may be arranged on an individual subject basis in discussion with the study medical monitor.

ANTI-BAN2401 ANTIBODY ASSESSMENT

Blood for anti-BAN2401 antibody assessment will be collected predose in a blinded fashion from all subjects during the treatment period at Visits 3, 9, 16, 22, 29, 35, and 42 and at the Early Termination Visit (if applicable) and the Follow-Up Visit, as specified in the Schedule of Assessments (Table 8) (revised per Amendments 01 and 08). Anti-BAN2401 antibodies will be processed in an ongoing basis. The PI is required to evaluate whether a subject has any infusion reactions or hypersensitivity to the study medication based solely on clinical findings and laboratory results from hematology, biochemistry and urinalysis, and to decide if the subject should be withdrawn from treatment or receive prophylactic medications prior to the next infusion based on these clinical assessments as outlined in the protocol.

PREGNANCY TEST

During the Randomization Phase, at study visits specified in Table 7 and Table 8 for the Core Study (revised per Amendment 08), urine samples for pregnancy tests will be taken from females of childbearing potential as defined in Section 9.3.1, Inclusion Criterion 12. Additionally, on the days on which PET scans take place, urine samples will be obtained from these subjects.

COLUMBIA-SUICIDE SEVERITY RATING SCALE

Subjects will be assessed for suicidal ideation and suicidal behavior using the C-SSRS according to the designed time points on the Schedule of Procedures/Assessments (Table 7, Table 8). A “yes” answer to type 4 or 5 suicidal ideation or a “yes” response to any suicidal behavior queries will trigger additional psychiatric evaluations by a psychiatrist to determine how the subject is to be managed clinically. All sites are required to identify a psychiatrist for referral purposes. The subject’s ability to continue to participate in the study will be determined by the investigator in consultation with the sponsor’s medical team. The types of C-SSRS forms will be specified in the eCRF or a separate manual to the protocol.

9.5.1.6 Other Assessments

AMYLOID PET AND CSF A β (1-42) ASSESSMENT (REVISED PER AMENDMENT 06)

Amyloid PET imaging or CSF A β (1-42) assessment will be used to confirm that all subjects with EAD have amyloid deposition in the brain. This criterion will allow for the definition of subjects with MCI due to AD – intermediate likelihood and will confirm amyloid pathology in mild Alzheimer’s disease dementia subjects. Florbetapir, flutemetamol, florbetaben, or any approved agent may be used in Canada, the EU, or any other region in which the study is conducted. For

screening purposes, the imaging agent of choice will be florbetapir at study sites in the US, while in other regions the choice of imaging agent will depend on local availability of imaging agent, thus allowing for use of florbetaben or flutemetamol as well as florbetapir. (revised per Amendment 07) While florbetapir is the preferred agent in the US, flutemetamol, florbetaben, or any approved agent may be used in the US if needed. For the longitudinal amyloid PET substudy in the Core Study, only florbetapir will be used in the US, while in other regions the choice of imaging agent will depend on local availability of the imaging agent, but the same tracer must be used across all PET assessments per subject. (revised per Amendment 07) Florbetapir, flutemetamol, florbetaben, or any approved agent may be used in Canada, the EU, or any other region in which the study is conducted (revised per Amendments 02 and 06). Certification of PET scanners, quality control, and analysis of the PET images will be performed by a central vendor. To determine eligibility at Baseline during the Prerandomization Phase, within 20 days after the Baseline Visit, each subject will undergo CSF A β (1-42) assessment or amyloid PET imaging with 1 of the aforementioned imaging agents. Eligibility will be based on a binary read (normal or abnormal) for PET, or a specified cut-off for CSF A β (1-42). (revised per Amendment 06)

Subjects may consent to both the PET and CSF assessments, but only need a positive amyloid result in only one of the 2 procedures to confirm eligibility (ie, even if one of the 2 results does not meet its respective eligibility criterion). Subjects who initially consent for only one of the amyloid screening assessments will only be allowed to subsequently consent for the second assessment should the first assessment result be positive or they have not yet been informed of the results of the first assessment (revised per Amendments 06 and 07). To determine eligibility for the study according to CSF A β (1-42) levels, a cutoff value for CSF A β (1-42) collected using single LP during the Baseline Visit will be applied. Subjects with CSF A β (1-42) levels less than this value will be eligible for the study. (revised per Amendment 06)

To determine whether or not the PET scan results allow the subject to remain eligible for the study, uptake patterns will be categorized as "normal" (ie, absence of amyloid deposition) or "abnormal" (ie, presence of amyloid deposition) by 2 independent readers, who will be blinded to each other's observations. Each reader will perform a qualitative visual read of the PET scans and will separately categorize subjects as having either "normal" or "abnormal" uptake on the basis of the PET image pattern. Readers will have been trained and certified to recognize brain PET images with abnormal or normal patterns of uptake. Inter rater and intra rater reliability will be assessed at regular intervals throughout the study.

Each subject's MRI scan will be warped into a template space and the same parameters will be applied to the subject's PET scan, resulting in alignment of the MRI and amyloid PET to the template. The template regions of interest will be then used to sample the warped PET images. Quantification of amyloid levels will be derived using an automated algorithm based on the standard uptake value ratio (SUVR) in the region of interest from 5 to 6 regions for each subject, including the precuneus, anterior cingulate gyrus, frontal lobe, parietal lobe, temporal lobe and the occipital lobe at Baseline and at 12 and 18 months of treatment. A weighted average from these regions in addition to regional values will be derived at baseline and longitudinal assessments.

Subjects who consent to participate in the imaging subgroup (n=306 total who complete 12 months of treatment in the Core Study) will undergo amyloid PET scans at Visits 29 and 42 (12 and 18 months). Duration of the PET scan and its timing relative to injection of the imaging agent will as per the imaging agent manufacturer's guidance (revised per Amendments 02 and 07). Subjects who participate in the imaging subgroup must undergo a baseline PET scan in this study (ie, historic PET scans are not allowed as baseline scans for the imaging subgroup).

Baseline CSF samples will be used for eligibility and for establishing the subject's baseline for the longitudinal assessment. CSF will be drawn via LP 2 to 4 days after the scheduled study Visit 29 (12 months). CSF samples should be collected predose on the day of the Visit 41 infusion. For those subjects who also consent to both CSF assessment and to amyloid PET, CSF should be collected 2 to 4 days after study drug infusion at Visit 29, and the amyloid PET procedure should be scheduled to take place on a separate day within 10 days of Visit 29 but after CSF collection. (revised per Amendment 06)

FUNCTIONAL ASSESSMENTS QUESTIONNAIRE (FAQ) (REVISED PER AMENDMENT 01)

On the basis of interviews with caregivers/informants or qualified partners, subjects will be rated for ability to carry out ten complex activities of daily living: 1) manage finances, 2) complete forms, 3) shop, 4) perform games of skill or hobbies, 5) prepare hot beverages, 6) prepare balanced meal, 7) follow current events, 8) attend to television programs, books, and magazines, 9) remember appointments, and 10) travel out of the neighborhood.³⁵ Each activity will be rated as 0 (normal, does without difficulty), 1 (has difficulty but does by self), 2 (requires assistance), or 3 (dependent). Scores will be summed across items to provide a total disability score (higher scores = greater impairment; maximum score = 30). If an activity was never or very rarely performed premorbidly, it will be marked as "Not Applicable" and will not be included in the score. A proportional score will be derived for subjects who mark any activity as 'Not Applicable' as follows (achieved score / (30 – 3 times the number of activities marked 'Not Applicable')

MEDICAL CLAIMS SUBSTUDY (REVISED PER AMENDMENT 16)

An optional medical claims substudy will be undertaken in the US only. The purpose of this substudy is to use medical claims data to further evaluate patterns of resource utilization and associated costs of care for subjects with EAD and their study partners. It will describe baseline characteristics of subjects with EAD for up to 5 years before study enrollment, for the duration of the Core Study, the duration of the period between the end of the Core Study and the Extension Baseline (if applicable), the duration of the Extension Phase (if applicable), and for up to 3 years after the end of the Core Study or Extension Phase (where applicable). The analyses will measure the evolution of care and the appearance of various diagnoses as subjects progress from MCI or Mild AD to other diagnoses. It will describe changes among subjects and study partners, in contrast to a comparison population consisting of a demographically matched cohort of non-EAD Medicare beneficiaries. A survey of study partners will provide supplemental information on the experience of those individuals who are responsible for the care of subjects with EAD. The survey data on burden to both subject and study partner health, utilization, and expenditure outcomes will be analyzed to explore the relationship between burden and subject/study partner health. The survey will assess current burden and lost productivity, perceived changes in burden with the

introduction of the new medication, attitudes regarding medication safety and cost, and use of respite programs in which study partners may be participating. The results of the medical claims substudy will be presented in a separate report. (revised per Amendments 16 and 17)

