9.7.1.1 Study Endpoints

PRIMARY ENDPOINT:

- Change from baseline in the ADCOMS at 12 months

KEY SECONDARY ENDPOINTS: (revised per Amendments 09 and 10)

- Change from baseline at 18 months in brain amyloid pathophysiology as measured by amyloid PET (revised per Amendments 09 and 10)
- Change from baseline in the ADCOMS at 18 months (revised per Amendment 09)
- Change from baseline in CDR-SB at 18 months (revised per Amendments 09 and 10)
- Change from baseline in ADAS-Cog at 18 months (revised per Amendments 09 and 10)
- Change from baseline in CSF biomarkers ($A\beta[1-42]$, t-tau, and p-tau) at 18 months (revised per Amendment 10)
- Change from baseline in total hippocampal volume at 18 months using vMRI (revised per Amendments 09 and 10)

SECONDARY ENDPOINTS: (revised per Amendments 09 and 10)

- Change from baseline at 12 months in brain amyloid pathophysiology as measured by amyloid PET (revised per Amendments 09 and 10)
- Change from baseline at 12 months on clinical status for the following assessments: ADCOMS, CDR-SB, and ADAS-Cog (revised per Amendment 10)
- Change from baseline in CSF biomarkers ($A\beta[1-42]$, t-tau, and p-tau) at 12 months (revised per Amendment 10)
- Change from baseline in total hippocampal at 6 and 12 months, and in left and right hippocampus, whole brain, and total ventricular volume as measured by vMRI at 6, 12, and 18 months (revised per Amendment 10)

EXPLORATORY ENDPOINTS:

- Change from baseline in clinical status at time points not analyzed in Key Secondary and Secondary sections for each of the following: ADCOMS, ADAS-Cog, CDR-SB, MMSE, and FAQ (revised per Amendment 10)

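### The printed FAQ rule puts subjects with a 'Not Applicable' activity on a 0–1 proportion and everyone else on a 0–30 sum, which all but removes the affected subjects' change from baseline

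*Protocol*

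**What the plan says.** The scoring rule is in Protocol Section 9.5.1.6, under the Functional Assessments Questionnaire. It rests on caregiver interviews in which "subjects will be rated for ability to carry out ten complex activities of daily living". The item scale is "Each activity will be rated as 0 (normal, does without difficulty), 1 (has difficulty but does by self), 2 (requires assistance), or 3 (dependent"). For a complete questionnaire, "Scores will be summed across items to provide a total disability score (higher scores = greater impairment; maximum score = 30").

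Activities outside the subject's former habits are handled separately: "If an activity was never or very rarely performed premorbidly, it will be marked as" not applicable and left out of the score. The total is then replaced: "A proportional score will be derived for subjects who mark any activity as" 'Not Applicable', with the formula printed as "achieved score / (30 – 3 times the number of activities marked" 'Not Applicable'). The text opens two brackets and closes one.

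Section 9.7.1.1 lists FAQ among the exploratory endpoints, under "Change from baseline in clinical status at time points not analyzed in Key Secondary and Secondary sections". Section 9.7.1.6 gives exploratory endpoints the same analysis as the key secondary endpoints, which is an MMRM. Tables 7 and 8 collect FAQ at Baseline and at Visits 9, 16, 22, 29, 35 and 42.

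**The concern.** The denominator in the proportional formula is exactly the highest sum attainable on the applicable activities, so the formula returns a fraction of the maximum. A complete questionnaire returns points out of 30. Nothing in the protocol brings the two onto a common scale before change from baseline is taken and modelled.

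This is not scoring detail left to the statistical analysis plan. The protocol prints an explicit formula, and a programmer who follows it obtains one variable in two units. At stake is the interpretability of FAQ, the study's dedicated daily-activities scale. For affected subjects the level says almost nothing about disability and the change says almost nothing about progression. The affected subjects are defined by their former habits, so they are not a random subset.

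**Working it through.** **Inputs, all from Section 9.5.1.6.** Ten activities; each rated 0 to 3; stated maximum 30; k = number of activities marked 'Not Applicable'; printed score for k ≥ 1 = achieved / (30 – 3k).

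**The protocol's own figure.** 10 × 3 = 30, which matches the stated maximum.

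**Range of the printed formula.** With k activities removed, the highest achievable sum is 3 × (10 – k) = 30 – 3k.

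| k | Highest achievable sum | Printed denominator | Maximum as printed | Maximum after × 30 |
|---|---|---|---|---|
| 1 | 27 | 27 | 1.0 | 30 |
| 2 | 24 | 24 | 1.0 | 30 |
| 3 | 21 | 21 | 1.0 | 30 |

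A subject fully dependent on all nine applicable activities scores 27/27 = 1.0. Beside a 0–30 sum, that reads as almost normal.

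**Case 1: same activity not applicable at every visit (expected under the rule).** A subject moves from 9 to 14 of 27.
- Printed: 14/27 – 9/27 = 5/27 = +0.19.
- Rescaled: 30 × 5/27 = +5.56.
- The ratio is exactly 30, because the two versions differ only by that factor.

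**Case 2: status switches between visits, average severity unchanged.** If all ten activities are rated at baseline with sum b, and one is marked not applicable later, the later printed score is 0.9b/27 = b/30. The change is b/30 – b = –(29/30)b, or –96.7% of b.
- b = 10: 9/27 – 10 = 0.33 – 10 = –9.67; the rescaled change is 30 × 9/27 – 10 = 0.
- Reverse switch, 9/27 at baseline and 10 later: +9.67; the rescaled change is again 0.

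**Effect on a group mean.** The protocol gives no frequency of 'Not Applicable' marks, so the share p is an assumption shown over a range. Assume baseline 10, a true change of +3 points for everyone on the 0–30 scale, and one activity affected.
- Stable status: mean = (1 – p) × 3 + p × 3/30.
- Newly marked after baseline: mean = (1 – p) × 3 + p × (13/30 – 10).

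| Share p | Stable status | Newly marked |
|---|---|---|
| 1% | 2.97 | 2.87 |
| 5% | 2.86 | 2.37 |
| 10% | 2.71 | 1.74 |
| 20% | 2.42 | 0.49 |

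In the stable case the mean is multiplied by 1 – 29p/30. If p is equal in both arms and unrelated to the size of the change, the treatment difference shrinks by the same factor: about 5% at p = 5% and 19% at p = 20%.

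**The case against.** **The formula may be truncated.** The unmatched opening bracket leaves room for a lost closing term such as ') × 30', dropped either in drafting or when the PDF was read. This is a fair point and cannot be settled from the text. Against it, the outer bracket may simply enclose the formula, and the label 'proportional score' fits a 0–1 result. In either case the sentence as it stands gives the wrong scale.

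**The mark should not change on study.** It depends on whether the activity was performed premorbidly, a fixed historical fact. This stands, and it decides what the main effect is. A reader might infer that one such activity routinely makes a subject look almost recovered. The document does not support that: the large false change (Case 2) needs the status to differ between visits, which would be a departure from the rule's own definition. The protocol does not, however, say that the baseline status is carried forward, so Case 2 is not excluded.

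**Other stronger readings.** A reader might take the rule to cover unanswered items; it covers only activities outside premorbid habit. A reader might also expect the mixed scale to inflate the variance. For a change score with stable status, the variance shifts by about p[(1 – p) × mean² – SD²], which is negative unless the mean change is around one SD or more. So no general inflation can be claimed.

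**FAQ carries little weight.** This also stands. It is exploratory only, supplies none of the 12 ADCOMS items (Section 9.7.1.6, Table 10), and enters no success or futility rule. Function is also rated in several CDR categories, and CDR-SB is a key secondary endpoint.

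**Conclusion.** The point holds on the text as printed. Section 9.5.1.6 defines FAQ on 0–30 for complete questionnaires and on 0–1 for any questionnaire with a 'Not Applicable' activity, and no other section reconciles the two.

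With stable status, affected subjects sit near the normal end at every visit and their change is one-thirtieth of its rescaled value. Under the even-distribution assumption in the working, this dilutes group means and treatment differences toward zero; the documents give no mechanism for a spurious benefit. A false change of about 97% of the score, in either direction, is confined to subjects whose status switches.

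The size at group level is unknown, because the share of affected subjects is not stated; the tabulated means are illustrations, not estimates. The primary and key secondary results are unaffected. The correction should be made because the rule is explicit and wrong as written and the remedy is small, but it does not bear on the trial's main conclusions.

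**What to change.** 1. State the score for subjects with any 'Not Applicable' activity as 30 × achieved score / (30 – 3 × number of activities marked 'Not Applicable'), with balanced brackets, so that every FAQ total lies on 0–30.
2. State that the 'Not Applicable' status set at Baseline is carried through all visits.
3. Confirm which formula the derivation program used. If it followed the printed text, re-derive FAQ and rerun the FAQ analyses, reporting how many subjects per arm had such an activity and whether any status changed on study.

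The text change is one factor and one sentence. Section 7.2.1.2 records the Core Study as complete by Amendment 11, and FAQ has no row in the Extension Phase schedules. The practical cost is therefore a program check and, if needed, a re-derivation of one exploratory endpoint. No new data are required.

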9.5.2 Schedule of Procedures/Assessments

9.5.2.1 Schedule of Procedures/Assessments

[Table 7](#) presents the Schedule of Screening and Baseline Procedures/Assessments for the Prerandomization Phase. [Table 8](#) presents the Schedule of Procedures/Assessments for Visits 3 through 27 (Panel A), and Visits 28 through 43, including the Follow-Up Visit (Panel B).

Further information regarding assessments in the Extension Phase Part A and Part B are provided in [Appendix 4](#) and [Appendix 5](#), respectively.

Table 7 Schedule of Screening and Baseline Procedures/Assessments (Visits 1 and 2), Study BAN2401-G000-201 – Core Study

	Phase	Prerandomization	
	Period	Screening	Baseline
	Visit	1	2
	Day	-60 to -31	-30 to -1
Procedures/ Assessments			
Informed consent	X		
Demographics	X		
Medical history (including AD history) (revised per Amendment 01)	X		
Inclusion/Exclusion	X		X
Vital signs	X		X
Height, weight, and BMI ^a	X		X
Complete physical exam	X		
Routine physical examination			X
12-lead ECG			X
Serum pregnancy test ^b	X		
Urine pregnancy test ^b			X
Blood for laboratory tests	X		X
Urinalysis (revised per Amendment 06)	X		X
Urine drug screen	X		
GDS	X		
MMSE ^c	X		X
WMS-IV LMI and LMII ^c	X		
CDR ^c	X		X
ADAS-Cog ^c			X
FAQ ^c			X
C-SSRS	X		X
Safety MRI ^d	X		
vMRI (for PD)	X		
Amyloid PET ^e			X
Blood for PG ^f			X
Blood for exploratory PD biomarker analysis			X
CSF sampling (for eligibility (revised per Amendment 06), PD and PK) ^g			X
Prior / concomitant meds including AChE inhibitors	X		X
Adverse events	X		X

Table 7 Schedule of Screening and Baseline Procedures/Assessments (Visits 1 and 2), Study BAN2401-G000-201 – Core Study

AChE = acetylcholinesterase, AD = Alzheimer’s disease, ADAS-Cog = Alzheimer’s Disease Assessment Scale-Cognitive subscale, BMI = body mass index, CDR = Clinical Dementia Rating, CSF = cerebrospinal fluid, C-SSRS = Columbia Suicide Severity Rating Scale, ECG = electrocardiogram, FAQ = Functional Assessment Questionnaire, GDS = Geriatric Depression Scale, MCI = mild cognitive impairment, MMSE = Mini-Mental State Examination, MRI = magnetic resonance imaging, PD = pharmacodynamic, PET = positron emission tomography, PG = pharmacogenomic, PK = pharmacokinetic, vMRI = volumetric MRI, WMS-IV LMI= Wechsler Memory Scale-Logical Memory (subscale) I, WMS-IV LM II= Wechsler Memory Scale-Logical Memory (subscale) II (revised per Amendment 01)

- a: Height measured only at Screening. BMI to be calculated at screening only.
- b: Pregnancy tests are only necessary for female subjects of childbearing potential. For those subjects, an additional urine pregnancy test must be done on the day of Amyloid PET scanning.
- c: Clinical assessments must be administered before any other screening assessments are conducted. These are to be completed in the morning whenever possible, or consistently at the same time of day. The order of assessments for the Screening Visit is as follows: MMSE, WMS-IV LMI and II, and CDR. will be administered to all subjects and subjects will be diagnosed as either MCI due to AD or mild Alzheimer’s disease dementia as defined by the protocol after completion of MMSE, WMS-IV LMI, WMS-IV LMII, and CDR. Once the diagnosis is made, the WMS-IV LMII inclusion criterion can be applied to all subjects. (revised per Amendment 06) The WMS-IV LMII is to be administered 20 to 30 minutes after the completion of LMI. Subject information should be collected in the 20 to 30 minutes between the WMS-IV LM I and LMII. Subjects who are considered ineligible for this study based on these assessments should not continue with the rest of the assessments for this visit. The order of assessments for the Baseline Visit is as follows: MMSE, CDR, ADAS-Cog, and FAQ. Caregivers/informants need to be present at the Screening and Baseline Visits. (revised per Amendment 01)
- d: For subjects who are approved for rescreening, safety MRI and vMRI need not be repeated if the date of the rescreen is <90 days from the date of the original screening MRI.
- e: Amyloid PET should be done at least 10 days before the planned randomization date. For those subjects who consent to CSF and PET eligibility assessments, CSF collection should always precede amyloid PET, and the 2 assessments should be separated by at least 24 hours. For these subjects, a positive amyloid result is needed for only one of the procedures to confirm eligibility (ie, even if one of the 2 results renders the subject ineligible). Subjects who initially consent for only one of the amyloid screening assessments will only be allowed to subsequently consent for the second assessment should the first assessment result be positive. Subjects who consent to Amyloid PET or CSF Amyloid are not required to participate in the respective substudies. For subjects who are approved for rescreening, the amyloid PET need not be repeated for eligibility if confirmed amyloid positive during the original screening procedure. If a rescreened subject will participate in the longitudinal PET substudy, quantitative PET collection should be repeated if the original PET collection was done >6 months from the date of the original screening procedure. (revised per Amendments 06 and 07) .
- f: For subjects who are approved for rescreening, pharmacogenetic testing need not be repeated if a sample was collected, processed, and *APOE4* results issued during the previous screening procedure. Great care must be taken to link the APOE status information with the new subject number.
- g: For those subjects who consent to the longitudinal CSF substudy, Baseline samples will be used for eligibility assessment and to establish a baseline measure for the longitudinal assessments. CSF should be collected at or after the Baseline Visit, and at least 19 days (21 days for sites in the Asia-Pacific region) before the planned randomization date. For those subjects who consent to both CSF and PET eligibility assessments, CSF collection should always precede amyloid PET, and the 2 assessments should be separated by at least 24 hours. For these subjects, a positive amyloid result is needed for only one of the procedures to confirm eligibility (ie, even if one of the 2 results renders the subject ineligible). For subjects who are approved for rescreening, the CSF need not be repeated for eligibility if confirmed amyloid positive during the original screening procedure. If a rescreened subject will participate in the longitudinal CSF sub-study, quantitative CSF collection should be repeated if the original CSF collection was done > 6 months from the date of the original screening procedure. (revised per Amendments 06 and 07) .

Table 8 Schedule of Procedures/Assessments, Core Study BAN2401-G000-201, Panel A, Visits 3 through 27, Weeks 1 through 49 – Core Study

Phase	Randomization																										
	Treatment																										
Period	3	4	5	6	7	8	9	10	11	12	13	14	15	16	17	18	19	20	21	22	23	24	25	26	27		
Visit ^a	3	4	5	6	7	8	9	10	11	12	13	14	15	16	17	18	19	20	21	22	23	24	25	26	27		
Week	1	3	5	7	9	11	13	15	17	19	21	23	25	27	29	31	33	35	37	39	41	43	45	47	49		
Procedures/ Assessments																											
Vital signs ^d	X	X	X	X	X	X	X	X	X	X	X	X	X	X	X	X	X	X	X	X	X	X	X	X	X		
Weight ^c	X						X							X						X							
Routine physical exam					X					X				X						X							
12-lead ECG					X					X				X						X							
Urine pregnancy test ^f							X							X						X							
Blood for laboratory tests ^g	X	X		X			X			X				X						X							
Urinalysis (revised per Amendment 06)	X	X		X			X			X				X						X							
MMSE ^h							X							X						X							
CDR ^h							X							X						X							
ADAS-Cog ^h							X							X						X							
FAQ ^h							X							X						X							
C-SSRS			X		X		X							X						X							
Safety MRI ⁱ					X		X							X						X							
Volumetric MRI (for PD) ^j					X		X							X						X							
Abbreviated MRI ^k				X																							
Informed consent ^l																											
Amyloid PET ^m																											
Randomization	X																										
Study drug administration	X	X	X	X	X	X	X	X	X	X	X ⁿ	X ⁿ	X ⁿ	X	X ⁿ	X	X ⁿ	X ⁿ	X ⁿ	X ⁿ							
Blood for serum BAN2401 PK ^o	X						X							X						X							
Blood for exploratory PD biomarker analysis																											
Blood for serum anti-BAN2401 ^p	X						X							X						X							
CSF sampling ^q																											
Prior / concomitant meds	X			X			X			X			X			X			X			X		X			
Adverse events	X	X	X	X	X	X	X	X	X	X	X	X	X	X	X	X	X	X	X	X	X	X	X	X			

Table 8 Schedule of Procedures/Assessments, BAN2401-G000-201, Panel B, Visits 28 through 43, Weeks 51 through 90 – Core Study

Phase Period	Randomization															Early Termination Visit ^b	Follow-Up Visit	Unscheduled Visit ^c	
	Treatment																		
Visit ^a	28	29	30	31	32	33	34	35	36	37	38	39	40	41	42		43	--	
Week	51	53	55	57	59	61	63	65	67	69	71	73	75	77	79		90		
Procedures/ Assessments																			
Vital signs ^d	X	X	X	X	X	X	X	X	X	X	X	X	X	X	X	X	X	X	X
Weight ^e		X						X										X	
Routine physical exam		X						X							X		X	X	X
12-lead ECG		X						X							X		X	X	X
Urine pregnancy test ^f		X						X							X		X		X
Laboratory tests ^g		X						X							X		X	X	X
Urinalysis (revised per Amendment 06)		X						X							X		X	X	X
MMSE ^h		X						X							X		X	X	
CDR ^h		X						X							X		X	X	
ADAS-Cog ^h		X						X							X		X	X	
FAQ ^h		X						X							X		X	X	
C-SSRS		X						X							X		X	X	X
Safety MRI ⁱ		X						X							X		X ⁱ	X	X
Volumetric MRI (for PD) ^j		X						X							X		X	X	X
Abbreviated MRI ^k																			
Informed consent ^l														X					
Amyloid PET ^m		X													X				
Randomization																			
Study drug administration	X ⁿ	X	X ⁿ	X	X ⁿ	X													
Blood for serum BAN2401 PK ^o		X						X							X		X		X
Blood for exploratory PD biomarker analysis		X													X				
Blood for serum anti-BAN2401 ^p		X						X							X		X	X	X
CSF sampling ^q		X													X				
Prior / concomitant meds			X			X			X			X		X		X	X	X	X
Adverse events	X	X	X	X	X	X	X	X	X	X	X	X	X	X	X	X	X	X	X

Table 8 Schedule of Procedures/Assessments, BAN2401-G000-201, Panel B, Visits 28 through 43, Weeks 51 through 90 – Core Study - Footnotes

ADAS-Cog = Alzheimer's Disease Assessment Scale-Cognitive subscale, AE = adverse event, ARIA = amyloid-related imaging abnormalities, CDR = Clinical Dementia Rating, CSF = cerebrospinal fluid, C-SSRS = Columbia Suicide Severity Rating Scale, ECG = electrocardiogram, EU = European Union, FAQ = Functional Assessment Questionnaire, LP = lumbar puncture, MMSE = Mini-Mental State Examination, MRI = magnetic resonance imaging, PD = pharmacodynamic, PET = positron emission tomography, PK = pharmacokinetic. (revised per Amendment 01)

- a: Assessments should take place on the first day of the study visit in the designated study week except as noted below (footnotes h, i, and j pertaining to imaging assessments, and [footnote o](#) pertaining to CSF sample collection). A visit window of ± 8 days will be allowed for each visit, except for Visit 3. A visit window of ± 7 days will be allowed for the Follow-Up Visit (Visit 43). (revised per Amendment 01)
- b: Subjects who discontinue the study or study drug early must comply with the Early Termination Visit (within 7 days after discontinuation the last dose of study drug) and the Follow-Up Visit (3 months after the last dose of study drug). They may also have unscheduled visits for safety assessments. Subjects who discontinue due to APOE status are expected to return for their Early Termination Visit and 3-month Follow-Up Visit (ie, 3 months after the last dose of study drug). Subjects who discontinue due to AE (including ARIA) are not allowed to rescreen for Study BAN2401-G000-201 (revised per Amendment 06). In addition, subjects who discontinue from study drug are expected to return after the Early Termination Visit for each scheduled visit when the clinical assessments of efficacy are to be conducted (Visits 9, 16, 22, 29, 35, and 42). At these visits clinical efficacy assessments (MMSE, CDR, ADAS-Cog, and FAQ) will be conducted and information on concomitant medications, AEs, and SAEs will be collected. Regularly scheduled clinical efficacy visits do not need to be attended if they fall within 8 days (visit window) of the Early Termination Visit or the 3-month Follow-Up Visit. Subjects who discontinue from study drug are considered on study as long as they return for their regularly scheduled clinical efficacy visits as outlined above. (revised per Amendment 01)
- c: Unscheduled visits may be conducted at any time that safety or safety MRI data indicate per protocol or as clinically indicated in the judgment of the investigator. Note that assessments indicated under Unscheduled Visits need not always be conducted – actual assessments needed will be determined by the investigator and will be based on the specific visit needs.
- d: Vital signs will be measured both at predose and after infusion. During Visits 3, 4, 5, and 6, vital signs should be recorded at least 2 hours after study drug infusion, in addition to predose. If at those visits no untoward effects of infusion on vital signs are detected ≥ 2 hours after infusion, these assessments at subsequent study visits may be conducted at a shorter interval after infusion. (revised per Amendment 06) -At visits where no infusion takes place (Visits 42 and 43), vital signs will be measured once. Vital sign measurements will consist of systolic and diastolic blood pressure (mmHg) measured after at least 3 minutes in a semi supine position, pulse (beats per minute), respiratory rate (per minute), and body temperature (in centigrade).
- e: Weight will be taken in the clinic at designated visits (Visits 3, 9, 16, 22, 29, 35, and 43). If a subject misses a clinic visit where weight is to be collected, subsequent visits should use the most recent, previous collected weight for infusion calculations until the next clinic visit. Under such circumstances, weight is to be taken at the next clinic visit and entered into the IVRS even if the visit is not designated for weight data collection.
- f: Females of childbearing potential only
- g: Blood for laboratory tests will be taken 4 hours after the end of infusion at Visit 3 and predose at all other visits as indicated.
- h: Scales are to be completed in the morning (or, if not possible, consistently at the same time of day) in the following order on the days indicated: MMSE, CDR, ADAS-Cog, and FAQ. Caregivers/informants (defined as a person able to support the subject for the duration of the study) need only to be present at visits where clinical assessment of MMSE, CDR, and ADAS-Cog takes place. (revised per Amendment 01)
- i: MRI imaging should be conducted at any time following the immediately preceding visit and prior to each of the following Visits according to the Schedule of Procedures/Assessments: Visits 7, 9, 16, 22, 29, 35, and 42 and at the Follow-Up Visit (Visit 43). The MRI may be conducted on the same day as the immediately preceding visit, after dosing at that visit. In all cases, the safety MRI must be reviewed by the imaging vendor and a local reader prior to a subject receiving the next dose of study drug. In the event of an Unscheduled Visit, the investigator in consultation with the sponsor will determine whether or not a safety MRI should be conducted. If an Early Termination Visit takes place, an MRI is to be conducted if not already performed during the preceding 90 days. (revised per Amendments 04, 06, and 07)
- j: A volumetric MRI sequence will be collected in ALL subjects immediately following all safety MRI assessments. Volumetric MRI data will be analyzed at the Screening Visit and at Visits 16, 29, and 42.
- k: The Visit 6 abbreviated MRI will be conducted at EU sites only, and should be conducted at any time following the immediately preceding visit (Visit 5) and prior to dosing at Visit 6. The Visit 6 MRI may be conducted on the same day as Visit 5 after subjects have been dosed. This abbreviated MRI will be comprised of a safety MRI to detect ARIA, lasting approximately 8 to 10 minutes. Volumetric MRI sequences will not be conducted at this visit. The safety MRI must be reviewed by the imaging vendor and a local reader prior to a subject receiving the next dose of study drug. In the event of an Unscheduled Visit, the investigator in consultation with the sponsor will determine whether or not a safety MRI should be conducted. If an Early Termination Visit takes place, an MRI is to be conducted if not already performed during the preceding 90 days. (revised per Amendment 07).
- l: Subjects can consent to enter the Extension Phase at this visit or any subsequent visit at which they are eligible. Subjects **must** consent to the longitudinal PET substudy for the Extension Phase to participate in the substudy. (revised per Amendment 11)

